#### 11.4 Liver function abnormalities related to regorafenib

For patients with observed worsening of serum liver tests considered related to regorafenib (i.e. where no alternative cause is evident, such as post-hepatic cholestasis or disease progression), the dose modification and monitoring advice in Table 6-5 should be followed.

Regorafenib is a UGT1A1 inhibitor. Mild, indirect (unconjugated) hyperbilirubinemia may occur in patients with Gilbert's syndrome.

Dose modifications/interruption for ALT and/or AST and/or bilirubin increases related to regorafenib						
Observed elevations a	1 st Occurrence	Restart	Re-occurrence			
Baseline G0 to G1 or baseline G1 to G2	Treat on time and check AST, ALT and bilirubin 2x/week for 2 weeks followed by weekly assessments for at least 4 weeks°.		Continue with therapy with monitoring at the investigator's discretion.			
Baseline G0 to G2	Delay until < G1 and check AST, ALT, bilirubin 2x/week.	Reduce 1 dose level and check AST, ALT, bilirubin weekly for at least 4 weeks. a, c	Discontinue			
Baseline any grade to G3	Delay until < G1 if baseline was G0 OR until G1 if baseline was G1 OR until G2 if baseline was G2.	Reduce 1 dose level and check AST, ALT, bilirubin weekly assessments for at least 4 weeks. a, c	Discontinue			
	Check AST, ALT, bilirubin 2x/week.					
	If ALT or AST > 8 x ULN with a concomitant rise in bilirubin (of any degree) compared to previous bilirubin values, consider permanent discontinuation at the first occurrence.					

a: Severity Grade per NCI-CTCAE v 4.0.

b: If ALT, AST, and bilirubin remain stable for two full cycles, dose re-escalation may be considered at the discretion of the investigator. After re-escalation, check ALT, AST, and bilirubin 2x/week for 2 weeks, then 1x/week for 4 weeks.

"G", abbreviation for "CTCAE v4.0 Grade".

c: This schedule of AST, ALT, and bilirubin monitoring need not be repeated for a given

IRB#: 13-244 A(9)

dose level if already completed once.

#### 12.0 CRITERIA FOR THERAPEUTIC RESPONSE/OUTCOME ASSESSMENT

Please refer to Section 10 regarding the timing of tumor measurement assessments.

Documentation (radiologic) must be provided for patients removed from study for progressive disease (not necessary if removed based on criteria for clinical progression). Objective responses should be confirmed with a second assessment performed at least 4 weeks later.

Response and progression will be evaluated in this study using the new international criteria proposed by the revised Response Evaluation Criteria in Solid Tumors (RECIST) guideline (version 1.1) [Eur J Ca 45:228-247, 2009]. Changes in the largest diameter (uni dimensional measurement) of the tumor lesions and the shortest diameter in the case of malignant lymph nodes are used in the RECIST criteria.

#### 12.1 Definitions

Evaluable for toxicity. All patients will be evaluable for toxicity from the time of their first treatment with regorafenib.

Evaluable for objective response. Only those patients who have measurable disease present at baseline and have received at least one dose of therapy will be considered evaluable for response. These patients will have their response classified according to the definitions stated below. (Note: Patients who exhibit objective disease progression prior to the end of cycle 1 will also be considered evaluable.)

Evaluable Non-Target Disease Response. Patients who have lesions present at baseline that are evaluable but do not meet the definitions of measurable disease, have received at least one cycle of therapy, and have had their disease reevaluated will be considered evaluable for non-target disease. The response assessment is based on the presence, absence, or unequivocal progression of the lesions.

#### 12.2 Disease Parameters

Measurable disease. Measurable lesions are defined as those that can be accurately measured in at least one dimension (longest diameter to be recorded) as  $\geq$ 20 mm by chest x-ray, as  $\geq$ 10 mm with CT scan, or  $\geq$ 10 mm with calipers by clinical exam. All tumor measurements must be recorded in millimeters (or decimal fractions of centimeters).

Note: Tumor lesions that are situated in a previously irradiated area are not considered measurable unless there has been demonstrated progression in the lesion.

Malignant lymph nodes. To be considered pathologically enlarged and measurable, a lymph node must be >15 mm in short axis when assessed by CT

(RB PB

IRB#: 13-244 A(9)

scan (CT scan slice thickness recommended to be no greater than 5 mm). At baseline and in follow-up, only the short axis will be measured and followed.

Non-measurable disease. All other lesions (or sites of disease), including small lesions (longest diameter <10 mm or pathological lymph nodes with ≥10 to <15 mm short axis), are considered non-measurable disease. Bone lesions, leptomeningeal disease, ascites, pleural/pericardial effusions, lymphangitis cutis/pulmonitis, inflammatory breast disease, and abdominal masses (not followed by CT or MRI), are considered as non-measurable.

Note: Cystic lesions that meet the criteria for radiographically defined simple cysts should not be considered as malignant lesions (neither measurable nor non-measurable) since they are, by definition, simple cysts.

'Cystic lesions' thought to represent cystic metastases can be considered as measurable lesions, if they meet the definition of measurability described above. However, if non-cystic lesions are present in the same patient, these are preferred for selection as target lesions.

Target lesions. All measurable lesions up to a maximum of 2 lesions per organ and 5 lesions in total, representative of all involved organs, should be identified as **target lesions** and recorded and measured at baseline. Target lesions should be selected on the basis of their size (lesions with the longest diameter), be representative of all involved organs, but in addition should be those that lend themselves to reproducible repeated measurements. It may be the case that, on occasion, the largest lesion does not lend itself to reproducible measurement in which circumstance the next largest lesion which can be measured reproducibly should be selected. A sum of the diameters (longest for non-nodal lesions, short axis for nodal lesions) for all target lesions will be calculated and reported as the baseline sum diameters. If lymph nodes are to be included in the sum, then only the short axis is added into the sum. The baseline sum diameters will be used as reference to further characterize any objective tumor regression in the measurable dimension of the disease.

Non-target lesions. All other lesions (or sites of disease) including any measurable lesions over and above the 5 target lesions should be identified as **non-target lesions** and should also be recorded at baseline. Measurements of these lesions are not required, but the presence, absence, or in rare cases unequivocal progression of each should be noted throughout follow-up.

#### 12.3 Methods for Evaluation of Measurable Disease

All measurements should be taken and recorded in metric notation using a ruler or calipers. All baseline evaluations should be performed as closely as possible to the beginning of treatment and never more than 4 weeks before the beginning of the treatment.

The same method of assessment and the same technique should be used to characterize each identified and reported lesion at baseline and during follow-up.

IRB#: 13-244 A(9)

Imaging-based evaluation is preferred to evaluation by clinical examination unless the lesion(s) being followed cannot be imaged but are assessable by clinical exam.

Clinical lesions: Clinical lesions will only be considered measurable when they are superficial (e.g., skin nodules and palpable lymph nodes) and ≥10 mm diameter as assessed using calipers (e.g., skin nodules). In the case of skin lesions, documentation by color photography, including a ruler to estimate the size of the lesion, is recommended.

Chest x-ray: Lesions on chest x-ray are acceptable as measurable lesions when they are clearly defined and surrounded by aerated lung. However, CT is preferable.

Conventional CT and MRI This guideline has defined measurability of lesions on CT scan based on the assumption that CT slice thickness is 5 mm or less. If CT scans have slice thickness greater than 5 mm, the minimum size for a measurable lesion should be twice the slice thickness. MRI is also acceptable in certain situations (e.g. for body scans).

Use of MRI remains a complex issue. MRI has excellent contrast, spatial, and temporal resolution; however, there are many image acquisition variables involved in MRI, which greatly impact image quality, lesion conspicuity, and measurement. Furthermore, the availability of MRI is variable globally. As with CT, if an MRI is performed, the technical specifications of the scanning sequences used should be optimized for the evaluation of the type and site of disease. Furthermore, as with CT, the modality used at follow-up should be the same as was used at baseline and the lesions should be measured/assessed on the same pulse sequence. It is beyond the scope of the RECIST guidelines to prescribe specific MRI pulse sequence parameters for all scanners, body parts, and diseases. Ideally, the same type of scanner should be used and the image acquisition protocol should be followed as closely as possible to prior scans. Body scans should be performed with breath-hold scanning techniques, if possible.

Ultrasound Ultrasound is not useful in assessment of lesion size and should not be used as a method of measurement. Ultrasound examinations cannot be reproduced in their entirety for independent review at a later date and, because they are operator dependent, it cannot be guaranteed that the same technique and measurements will be taken from one assessment to the next. If new lesions are identified by ultrasound in the course of the study, confirmation by CT or MRI is advised. If there is concern about radiation exposure at CT, MRI may be used instead of CT in selected instances.

Endoscopy, Laparoscopy The utilization of these techniques for objective tumor evaluation is not advised. However, such techniques may be useful to confirm complete pathological response when biopsies are obtained or to determine relapse in trials where recurrence following complete response (CR) or surgical resection is an endpoint.

IRB#: 13-244 A(9)

Tumor markers Tumor markers alone cannot be used to assess response. If markers are initially above the upper normal limit, they must normalize for a patient to be considered in complete clinical response. Specific guidelines for both CA-125 response (in recurrent ovarian cancer) and PSA response (in recurrent prostate cancer) have been published [*JNCI* 96:487-488, 2004; *J Clin Oncol* 17, 3461-3467, 1999; *J Clin Oncol* 26:1148-1159, 2008]. In addition, the Gynecologic Cancer Intergroup has developed CA-125 progression criteria which are to be integrated with objective tumor assessment for use in first-line trials in ovarian cancer [*JNCI* 92:1534-1535, 2000].

Cytology, Histology These techniques can be used to differentiate between partial responses (PR) and complete responses (CR) in rare cases (e.g., residual lesions in tumor types, such as germ cell tumors, where known residual benign tumors can remain).

The cytological confirmation of the neoplastic origin of any effusion that appears or worsens during treatment when the measurable tumor has met criteria for response or stable disease is mandatory to differentiate between response or stable disease (an effusion may be a side effect of the treatment) and progressive disease.

#### 12.4 Response Criteria

#### 12.4.1 Evaluation of Target Lesions

Complete Response (CR): Disappearance of all target lesions. Any

pathological lymph nodes (whether target or nontarget) must have reduction in short axis to <10

mm.

Partial Response (PR): At least a 30% decrease in the sum of the

diameters of target lesions, taking as reference

the baseline sum diameters.

Progressive Disease (PD): At least a 20% increase in the sum of the

diameters of target lesions, taking as reference the smallest sum on study (this includes the baseline sum if that is the smallest on study). In addition to the relative increase of 20%, the sum must also demonstrate an absolute increase of at least 5 mm. (Note: the appearance of one or

more new lesions is also considered

progressions).

Stable Disease (SD): Neither sufficient shrinkage to qualify for PR nor

sufficient increase to qualify for PD, taking as reference the smallest sum diameters while on

study.

(RB PB

IRB#: 13-244 A(9)

#### 12.4.2 Evaluation of Non-Target Lesions

Complete Response (CR): Disappearance of all non-target lesions and

normalization of tumor marker level. All lymph nodes must be non-pathological in size (<10 mm short axis). Note: If tumor markers are initially

above the upper normal limit, they must normalize for a patient to be considered in

complete clinical response.

Non-CR/Non-PD: Persistence of one or more non-target lesion(s)

and/or maintenance of tumor marker level above

the normal limits.

Progressive Disease (PD): Appearance of one or more new lesions and/or

unequivocal progression of existing non-target lesions. Unequivocal progression should not normally trump target lesion status. It must be representative of overall disease status change,

not a single lesion increase.

Although a clear progression of "non-target" lesions only is exceptional, the opinion of the treating physician should prevail in such circumstances, and the progression status should be confirmed at a later time by the review panel (or Principal Investigator).

#### 12.4.3 Evaluation of Best Overall Response

The best overall response is the best response recorded from the start of the treatment until disease progression/recurrence (taking as reference for progressive disease the smallest measurements recorded since the treatment started). The patient's best response assignment will depend on the achievement of both measurement and confirmation criteria.

#### For Patients with Measurable Disease (i.e., Target Disease)

Target Lesions	Non-Target Lesions	New Lesions	Overall Response	Best Overall Response when Confirmation is Required*
CR	CR	No	CR	>4 wks. Confirmation**
CR	Non- CR/Non-PD	No	PR	>4 wks. Confirmation**
CR	Not evaluated	No	PR	
PR	Non- CR/Non- PD/not evaluated	No	PR	
SD	Non- CR/Non- PD/not evaluated	No	SD	Documented at least once ≥4 wks. from baseline**

IRB PB

IRB#: 13-244 A(9)

PD	Any	Yes or No	PD	no prior SD, PR or CR
Any	PD***	Yes or No	PD	'
Any	Any	Yes	PD	

See RECIST 1.1 manuscript for further details on what is evidence of a new

Note: Patients with a global deterioration of health status requiring discontinuation of treatment without objective evidence of disease progression at that time should be reported as "symptomatic deterioration." Every effort should be made to document the objective progression even after discontinuation of treatment.

#### For Patients with Non-Measurable Disease (i.e., Non-Target Disease)

Non-Target Lesions	New Lesions	Overall Response
CR	No	CR
Non-CR/non-PD	No	Non-CR/non-PD*
Not all evaluated	No	not evaluated
Unequivocal PD	Yes or No	PD
Any	Yes	PD

\* 'Non-CR/non-PD' is preferred over 'stable disease' for non-target disease since SD is increasingly used as an endpoint for assessment of efficacy in some trials so to assign this category when no lesions can be measured is not advised

### 12.4.4 Duration of Response

Duration of overall response: The duration of overall response is measured from the time measurement criteria are met for CR or PR (whichever is first recorded) until the first date that recurrent or progressive disease is objectively documented (taking as reference for progressive disease the smallest measurements recorded since the treatment started).

The duration of overall CR is measured from the time measurement criteria are first met for CR until the first date that progressive disease is objectively documented.

Duration of stable disease: Stable disease is measured from the start of the treatment until the criteria for progression are met, taking as reference the smallest measurements recorded since the treatment started, including the baseline measurements.

Only for non-randomized trials with response as primary endpoint.

\*\*\* In exceptional circumstances, unequivocal progression in non-target lesions may be accepted as disease progression.

IRB#: 13-244 A(9)

### 12.4.5 6-month Progression-Free Survival

Proportion of patients alive and free of progression at 6 months.

#### 13.0 CRITERIA FOR REMOVAL FROM STUDY

- Disease progression on treatment with regorafenib
- Patients may be removed from the study for protocol non-compliance.
- If at any time the patient develops unacceptable toxicity he/she will be removed from study.
- Participants can be removed from the study at any time if the study doctor feels that it is in their best interest to do so.
- Patients may withdraw consent from the study at any time.

#### 14.0 BIOSTATISTICS

Two co-primary objectives will be evaluated: best overall response rate (BOR; CR+PR by RECIST v1.1 observed at any time between start of treatment and patient's removal from the study) and 6-month PFS (proportion of patients alive and progression-free at 6 months). If either one of these objectives is met, the treatment would be considered worthy of further investigation.

Our recent literature review of all systemic chemotherapy studies reported for R/M ACC patients from 1966 to 2009 revealed that these were generally small studies of variable, poor methodological quality from which definitive conclusions regarding the efficacy of chemotherapy are difficult to establish. Objective responses with cytotoxic chemotherapy were infrequent, and in 10 studies evaluating different targeted agents (imatinib, gefitinib, cetuximab, lapatinib, bortezomib) involving 157 ACC patients, only 2 objective responses were reported (in response to high dose imatinib). Notably, there is no data addressing potential efficacy of systemic therapy beyond the first line setting in R/M ACC. Therefore, we will adopt a null hypothesis of BOR of 5% and an expected BOR of 20% as the alternative hypothesis. In order to demonstrate that the BOR in the studied population is >5% with a one-sided type I error of 5% and power of 90%, at least 5 responses need to be observed among 38 patients enrolled.

Among all published phase II single-agent trials performed in recurrent/metastatic ACC, we identified six studies involving 106 patients that reported a 6-month progression-free survival (PFS) with single-agent therapy (imatinib, cetuximab, gemcitabine, paclitaxel, lapatinib, and sunitinib). The mean 6-month PFS from these studies was 40.1%. Three of these studies did not require evidence of radiographic or clinical disease progression for study entry; of the remaining three studies, two required evidence of RECIST progression or clinical deterioration within 6 months and the other study required symptomatic and/or progressive disease by undefined criteria. Based on these studies, we will adopt a null hypothesis for 6-month PFS of 40% and an expected 6-month PFS of 65% as the alternative hypothesis. In order demonstrate that 6-month PFS in the

IRB PB

IRB#: 13-244 A(9)

studied population is > 40% with a one-sided type I error of 5% and power of 90%, at least 21 of the 38 patients enrolled need to be alive and free of progression at the 6-month time point (exact binomial design).

Assuming that 6-month PFS and BOR are independent, the overall type 1 error is <0.1. The type 1 error decreases very slightly if PFS and BOR are positively correlated.

Patients who receive at least one dose of medication will be included in the evaluation of the primary objectives. Patients who do not have a recorded CR or PR and are removed from the study without a final radiologic evaluation will be classified as non-responders for BOR evaluation. If patients discontinue the study before the 6-mo PFS evaluation without evidence of progression, every effort will be made to bring them in for a 6-mo radiologic evaluation. If this is not possible, the patients will be classified as progressors for the purpose of the 6-month PFS evaluation.

The secondary endpoint is the evaluation of safety/tolerability of regorafenib.

Safety will be assessed in terms of AEs, laboratory data and vital sign data, which will be collected for all patients. Appropriate summaries of these data will be presented. AE will be listed individually per patient according to CTCAE version 4.0, and the number of patients experiencing each AE will be summarized. The safety population will comprise all patients who receive at least one dose of study treatment.

Due to the limited sample size, the analyses investigating the association between correlative markers and response to therapy will be exploratory. Levels of c-kit, VEGF, VEGFR, PDGF, PDGFR, in archival tumor tissue will be quantified by immunohistochemistry (IHC) and their association with objective response to regorafenib will be investigated using the non-parametric Wilcoxon rank-sum test. Similarly, association between c-myb (strong staining, 2+ vs other) or t(6;9) translocation and response will be tested using Fisher's exact test.

We will investigate, in an exploratory fashion, whether gene alterations that we detect are associated with response. Further, we will use linear models for microarray data (LIMMA), which performs moderated t-tests by discounting changes in low expressing genes with low variance, to identify genes who are differentially expressed between responders and non-responders. Multiplicity correction will be undertaken by controlling the false discovery rate.

We anticipate an accrual rate of approximately 2-3 patients/month; therefore we expect accrual to be completed within 15 months.

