#### 6.2 Subject Exclusion Criteria

- Concurrent anti-cancer therapy (chemotherapy, definitive radiation therapy, surgery, immunotherapy, biologic therapy, or tumor embolization) other than study treatment.
   Concurrent therapy with bisphosphonates or denosumab for bone metastases is allowed.
   Palliative radiation to non-target lesions is also allowed.
- Prior use of regorafenib.
- Uncontrolled hypertension (systolic pressure >140 mm Hg or diastolic pressure > 90 mm
   Hg [NCI-CTCAE v4.0] on repeated measurement) despite optimal medical management.
- Concurrent use of another investigational drug or device therapy (i.e., outside of study treatment) during, or within 4 weeks of trial entry (signing of the informed consent form).
- Concurrent use of strong CYP3A4 inhibitors (e.g. clarithromycin, grapefruit juice, itraconazole, ketoconazole, nefazodone, posaconazole, telithromycin, and voriconazole). or strong CYP3A4 inducers (e.g. rifampin, phenytoin, carbamazepine, phenobarbital, and St. John's Wort).
- Use of any herbal remedy (e.g. St. John's wort [Hypericum perforatum])

IRB PB

IRB#: 13-244 A(9)

- Major surgical procedure, open biopsy, or significant traumatic injury within 28 days before start of study medication.
- Active or clinically significant cardiac disease including:
  - Congestive heart failure New York Heart Association (NYHA) > Class II.
  - Active coronary artery disease that is not medically treated.
  - Cardiac arrhythmias requiring anti-arrhythmic therapy other than beta blockers or digoxin.
  - Unstable angina (anginal symptoms at rest), new-onset angina within 3 months before randomization, or myocardial infarction within 6 months before randomization.
- Therapeutic anticoagulation with Vitamin-K antagonists (e.g., warfarin) is not allowed if the
  medication dose and/or INR/PTT are not considered stable by the treating physician. If
  the dose and/or INR/PTT are stable, therapeutic anticoagulation with Vitamin-K
  antagonists is allowed with close monitoring. Anticoagulation with heparin or heparinoids
  is allowed.
- Evidence or history of bleeding diathesis or coagulopathy.
- Any hemorrhage or bleeding event ≥ NCI CTCAE Grade 3 within 4 weeks prior to start of study medication.
- Subjects with thrombotic, embolic, venous, or arterial events, such as cerebrovascular
  accident (including transient ischemic attacks) deep vein thrombosis or pulmonary
  embolism within 6 months of start of study treatment.

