	a: See Section 8.0 for the timing of these tests/evaluations prior to the start of therapy. b: Patients will start the study taking regorafenib 120 mg orally daily for 3 weeks in a 4 week cycle. Patients for whom regorafenib dose reduction was not performed or required may have their treatment dose increased to the FDA-approved dose of 160 mg daily orally for 3 weeks in a 4-week cycle in cycle #2 or beyond (this is not mandatory). If a patient misses a dose of regorafenib for personal reasons (i.e. forgetting to take medication, nausea, etc.), the missed dose should be documented on the patient's pill diary (Appendix B). Missed doses not directed by the investigator(s) that constitute ≤ 20% of the mandated doses for a given cycle will not be considered (a) protocol violation(s). Doses held at the discretion of the physician are never protocol violations. Missed or skipped doses will not be made up (i.e., the week/day count on therapy will continue regardless of whether doses												

IRB#: 13-244 A(9)

have been missed or skipped).

- c: Albumin, alkaline phosphatase, total bilirubin, bicarbonate, BUN, calcium, chloride, creatinine, glucose, LDH, phosphorus, potassium, total protein, SGOT [AST], SGPT [ALT], sodium.
- d: These Week 1 evaluations may be performed up to 3 days prior to the start of treatment.
- e: These Week 1 laboratory tests may be done up to 7 days prior to starting treatment. It is unnecessary to repeat these laboratory tests if the screening assessments of the same tests were performed within 7 days prior to the first dose of therapy.
- f: After the completion of Cycle 2, the CBC, serum chemistry blood tests, coagulation studies (if required), physical examinations, vitals signs, performance status, and weight will be done once every cycle, preferably on week 1 of every cycle. If the patient cannot be seen on week 1, these evaluations may be completed up to 1 week prior or during another week within the cycle at the discretion of the treating physician.
- g: Off-study evaluation will be performed within 30 days of the patient's last dose of regorafenib.

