### Alternatives/options

Participation in this trial is voluntary. Depending on the specific details of the situation, patient options without being in a study might include:

- Other palliative chemotherapy off study.
- Participation in a different clinical trial
- · Best supportive care

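### 6-month PFS scores early discontinuers by a recalled scan with no condition on other systemic anticancer therapy started in the meantime

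*Combined protocol and SAP*

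**What the plan says.** Section 12.4.5 defines the endpoint as "Proportion of patients alive and free of progression at 6 months". Section 14.0 counts every patient who has taken at least one dose and gives a two-step rule for those who stop early. First: "If patients discontinue the study before the 6-mo PFS evaluation without evidence of progression, every effort will be made to bring them in" for a radiologic evaluation at 6 months. Second: "If this is not possible, the patients will be classified as progressors for the purpose of the 6-month PFS evaluation".

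Patients can leave without progression. Section 13.0 lists non-compliance, the study doctor's judgement, withdrawal of consent, and toxicity: "If at any time the patient develops unacceptable toxicity he/she will be removed from study".

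The other co-primary endpoint, best overall response (BOR), has a closing point. It counts responses "observed at any time between start of treatment and patient's removal from the study". The 6-month PFS endpoint has no such limit.

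On other anticancer treatment, Section 6.2 excludes "Concurrent anti-cancer therapy (chemotherapy, definitive radiation therapy, surgery, immunotherapy, biologic therapy, or tumor embolization) other than study treatment". That concerns treatment given alongside regorafenib, not treatment started after it. The Study Calendar lists concurrent medications up to the off-study visit, and footnote g says "Off-study evaluation will be performed within 30 days of the patient's last dose of regorafenib".

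Either endpoint alone makes the regimen worthy of further investigation: at least 21 of 38 alive and progression-free at 6 months, or at least 5 of 38 responding.

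**The concern.** Take a patient who stops regorafenib early for toxicity, starts another systemic drug, returns at month 6 and has no RECIST progression. Followed as written, the plan scores this patient as a success. In a single-arm trial, the part that the second drug played in that scan cannot be separated from the part that regorafenib played.

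The two co-primary endpoints also differ without explanation. A response on a later drug cannot count for BOR, but stability on a later drug can count for PFS.

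Scoring by scan whatever therapy follows is a recognised choice, but the plan does not state it as one. Its effect may also be hard to examine afterwards, because no recording of new therapy is scheduled between the off-study visit and month 6. Case report forms are not among the documents, so they may capture it.

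At stake is a go/no-go rule with little slack, in which 6-month PFS alone is enough for a positive conclusion.

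**Working it through.** **Inputs (Sections 4.1 and 14.0).** N = 38. PFS: null 40%, alternative 65%, success at 21 or more. BOR: null 5%, alternative 20%, success at 5 or more. Each is one-sided at 5% with 90% power. Overall error is stated as below 0.1, assuming independent endpoints.

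**The plan's own figures, exact binomial.**
- PFS: P(X ≥ 21 | 38, 0.40) = 0.0409; power P(X ≥ 21 | 38, 0.65) = 0.921.
- BOR: P(X ≥ 5 | 38, 0.05) = 0.0397; power P(X ≥ 5 | 38, 0.20) = 0.901.
- Overall error: 1 − (1 − 0.0409)(1 − 0.0397) = 0.079.

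The design reproduces. A cut-off of 20 would give a PFS error of 0.078, so 21 is the smallest valid cut-off.

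**Assumed number of affected patients.** The documents give no rate of early discontinuation or of later therapy. Let k of the 38 be early stoppers on another drug whose scan turns a failure into a success, with a true rate of 40% when they count as failures. Three ways to model k:
- A, k as an expected number: p = 0.40 + k/38, which is 0.4263 for k = 1 and 0.4526 for k = 2; the error is P(X ≥ 21 | 38, p).
- B, exactly k, overall true rate held at 40%: the other 38 − k succeed at 0.40 × 38/(38 − k), which is 0.4108 and 0.4222; the error is P(X ≥ 21 − k | 38 − k).
- C, exactly k, the others at 40%: the error is P(X ≥ 21 − k | 38 − k, 0.40). For k = 1 the overall true rate is then 0.40 × 37/38 = 38.9%, slightly inside the null.

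Overall error = 1 − (1 − PFS error)(1 − 0.0397).

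| Model | PFS error, k = 1 | Overall, k = 1 | PFS error, k = 2 | Overall, k = 2 |
|---|---|---|---|---|
| A | 0.080 | 0.116 | 0.141 | 0.175 |
| B | 0.076 | 0.113 | 0.133 | 0.167 |
| C | 0.059 | 0.096 | 0.083 | 0.119 |

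**Partial conversion.** If one such patient has only a 50% chance of being turned from failure to success, the expected number is 0.5 and p = 0.40 + 0.5/38 = 0.4132. PFS error is 0.058 and overall error 0.095. Under model A the overall error reaches 0.10 at an expected 0.62 patients.

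**Opposite effect.** If an expected one progression-free patient is scored as a progressor for lack of a scan, p = 0.40 − 1/38, PFS error is 0.019 and overall error 0.058. An expected one in each direction cancels.

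**The case against.** The strongest reply is that the plan already gives every dosed patient a score. The endpoint is RECIST-based, discontinuers are recalled, and those without a scan are failures. Section 12.4.3 also asks that objective progression be documented after treatment stops. Read together, these point to scan-based follow-up, which is legitimate. This stands in part: the recall rule is clear, but it is silent on new therapy, and silence does not show that the case was considered.

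The magnitude is also open to challenge. Models A to C move each affected patient from certain failure to certain success. A patient who would have been progression-free anyway is not a distortion, and Section 3.0 describes systemic therapy in this disease as of limited effectiveness. This stands. It would be tempting to say that a single patient breaks the stated overall error of below 0.1. That holds under models A and B, but not under C (0.096) or with 50% conversion (0.095).

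Two further readings go beyond the documents. A reader might infer that bias favours regorafenib overall, but the no-scan rule pushes the other way and neither rate is known. A reader might also take "Other palliative chemotherapy off study" in Section 17.0 as evidence that early stoppers will receive other drugs. That list gives alternatives to taking part and does not describe care after discontinuation.

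Finally, scoring these patients as failures could itself create a mismatch with the historical 40%, because the scoring rules of the six studies behind it are not in the documents. That is a reason to state the choice and to report both scorings.

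**Conclusion.** The concern holds as a gap in a primary endpoint rule. A progression-free scan obtained on another systemic therapy counts toward 21 of 38, and nothing in the plan prevents, records or separately reports this. The sample size, cut-offs and stated error and power figures are otherwise sound.

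The size is uncertain. One such patient takes the overall error to between 0.096 and 0.116 (0.095 if conversion is only 50% likely), and two take it to between 0.119 and 0.175. These ranges rest on an assumed number of patients, a true rate of 40% or just below with those patients counted as failures, and independent endpoints. If the historical 40% was scored by scan regardless of later therapy, there is no inflation. The point should be settled before the data are read. It does not show that the trial's conclusion would be wrong.

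**What to change.** 1. Record any new systemic anticancer therapy and its start date up to month 6.
2. In Sections 12.4.5 and 14.0, state that a patient who starts other systemic anticancer therapy before the 6-month evaluation is scored as not progression-free.
3. Report scan-based scoring as a sensitivity analysis, with the number of such patients and whether 21 of 38 is met under each scoring.

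If the sponsor prefers scan-based scoring as primary, state that choice and pre-specify failure scoring as the sensitivity analysis. N, the 21 of 38 cut-off, the recall scan and the no-scan rule stay as they are.

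**Cost.** One sentence in two sections, one data item and one extra analysis. Observed 6-month PFS may be slightly lower. If the 65% alternative counted such patients as successes, one of them reduces PFS power from 0.921 to P(X ≥ 21 | 38, 0.65 − 1/38) = 0.858, below the planned 90%.

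The power to succeed on either endpoint, 1 − (1 − PFS power)(1 − BOR power) under independence, falls less. It goes from 0.992 to 0.986 if the true BOR is 20% (BOR power 0.901). It goes from 0.954 to 0.916 if the true BOR is 11% (BOR power 0.408), the approximate response rate that Section 3.0 reports for sorafenib and dovitinib.
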